7.1. Table of Events

Study Visit	Enrollment	Baseline				Condition 1			Wash- out			Condition 2			P4 daily administration
		wk1	Wk2	Wk3	Wk4	Wk1	Wk2	Wk3	Wk 1	Wk2	Wk3	Wk 1	Wk2	Wk3	
Visit						_		_			4.0		4.0		
Number:	0	1	2	3	4	5	6	7	8	9	10	11	12	13	14
Informed	X														
consent	.,									1					
Medical &	Х														
cancer Hx	V				V	V	V	V	V	V	V	V	V	V	V
Side effects	X				Х	Х	Х	Х	X	Х	Х	Х	Х	Х	Х
Vitals and Weight	X														
MINI	Х														
Stressful	Х														
Events															
IDAS	Χ	X	Χ	Χ	Χ	Χ	Χ	Χ	Χ	Х	Χ	X	Χ	Χ	
Daily Irritability		Х	Х	Х	Х	X	Х	Х	Х	Х	Х	X	Х	Х	
Urinary E1G		Х	Х	Х	Х			Х							
Tasks (EEG)															
Dot Probe					Х			Х						Х	
Affective Posner Paradigm					Х			Х						Х	
BIS-BAS and FNR					Х			Χ						Х	
Green Climacteric Scale	Х				Х			Х						Х	
PSQI	Х				Χ			Χ						Х	
P4															Х

MINI - Mini International Neuropsychiatric Interview

Stressful Events – assessed via the Life Events Survey will assess moderate to severe events in the preceding six months

IDAS – Inventory of Depression and Anxiety Symptoms

Daily Irritability - assessed using the irritability subscale of the IDAS

Urinary E1G – assessed every other day over the baseline period and the last week of each condition

Dot Probe task - assesses threat

Affective Posner Paradigm – assesses frustration to non-reward

BIS-BAS and FNR – Inhibition/Behavioral Activation Scales

FNR – Frustrative non-reward Responsiveness Subscale

PSQI – Pittsburgh Sleep Quality Index

7.2. Screening

Participants will undergo an initial pre-screening within 30 days of enrollment (days -30 through day -1). We will obtain verbal consent over the phone for this initial pre-screening. A negative screening mammogram will be acquired during the 30-day prescreening window as part of pre-screening. Additional pre-screening by phone will include assessing medication use, medical history, bleeding pattern history, and irritability symptoms. If the participant meets all pre-screening criteria, an enrollment visit will be scheduled.

Consistent with clinical practice as per consultation with [name], study gynecologist, and current opinion⁴⁶ we will not require a gynecological screening exam for our participants for the following reasons: 1) each is medically healthy with no chronic medical conditions; 2) each will have a normal screening mammogram within the preceding 24 months; 3) each is of normotensive blood pressure status; 4) each has no more than base rate risk for ovarian or endometrial cancer; and 5) each is in the early menopause transition and therefore having semi-regular menstrual periods (within +/- 7 days difference in cycle length from premenopausal cycle length). If, however, a woman reports at screening that her menstrual bleeding lasts longer than seven days or her bleeding is profuse ('flooding' or soak through protection), [name] will perform a screening endometrial ultrasound to confirm eligibility based on thickness of the endometrium. Those participants with any evidence of endometrial hyperplasia will be withdrawn and referred for gynecological care.

7.3. Enrollment

During the enrollment session (Visit 0) the following sequence of events will occur:

- Obtaining informed written consent will involve a six-step process: 1) Participant reads consent form;
 Research staff answer questions; 3) Research staff asks participant to summarize risks associated with the research; 4) Research Staff asks if participant wishes to speak the PIs; 5) participant signs consent form witnessed by research staff member; and 6) participant receives a copy of the signed consent form.
- 2. Participants complete the Personal and Family Medical History Questionnaire (PFHQ) which includes the Cancer History Questionnaire. These will be reviewed in real time. The side effects checklist will be administered that includes detailed questions on bleeding patterns, indicators of deep vein thrombosis, and mood in order to obtain baseline levels of these indicators. Weight and vitals will also be obtained. If ineligible, based on any of these assessments, the enrollment session will be concluded and the participant withdrawn.
- 3. Baseline questionnaires will be administered to assess menopausal symptoms (Green Climacteric Scale) and Sleep Quality (PSQI).

7.4. Study Visits

Visit 0: Enrollment session. During the enrollment session (Day 0) the following sequence of events will occur:

1. Obtain informed written consent using a six-step process: 1) Participant reads consent form; 2) Research staff answer questions; 3) Research staff asks participant to summarize risks associated with the research; 4) Research Staff asks if participant wishes to speak to the PIs; 5) participants signs

- consent form witnessed by research staff member; and 6) participant receives a copy of the signed consent form.
- 2. Participants complete the Personal and Family Medical History Questionnaire and the Cancer History Questionnaire that will be reviewed in real time. If ineligible, based on medical history or concomitant medication use, the enrollment session will be concluded and the participant withdrawn.
- 3. The MINI interview is conducted by a trained staff member.
- 4. Baseline questionnaires will be administered to assess menopausal symptoms (Green Climacteric Scale) and Sleep Quality (PSQI).

Visits 1 - 4 (weeks 1 - 4 of the baseline phase).

- 1. Weekly assessment of mood using the CES-D questionnaire participants will be prompted to complete this questionnaire at home using the HIPAA compliant REDCap software
- 2. Daily assessment of irritability symptoms using the irritability subscale of the IDAS questionnaire participants will be prompted to complete this questionnaire at home using the HIPAA compliant Redcap software
- 3. Participants collect E1G using urine strips every other day during weeks 1 4 of baseline. Research staff visit the home to retrieve samples at the end of each week
- 4. Side effects assessed in person at week 4 of baseline during home visit to collect urine samples in order to provide an additional comparator of baseline, pre-intervention symptoms
- 5. Participants visit the laboratory at the end of baseline week 4 (+/- 2 days from day 28 of the baseline phase) and undergo EEG testing with Dot Probe and the Affective Posner Paradigm

Visits 5-7 (weeks 1 – 3 of Condition 1)

- 1. Side effects will be assessed at the end of each week in Condition 1 either via phone (weeks 1 and 2) or in person during the home visit to collect the urine strips (week 3).
- 2. Weekly assessment of mood using the IDAS questionnaire participants will be prompted to complete this questionnaire at home using the HIPAA compliant Redcap software
- Daily assessment of irritability symptoms using the irritability subscale of the IDAS questionnaire participants will be prompted to complete this questionnaire at home using the HIPAA compliant
 Redcap software
- 4. At the end of week 3 of Condition 1, participants visit the lab in person at the end of baseline week 4 (+/- 2 days from day 21 of the Condition 1) and undergo EEG testing with Dot Probe and the Affective Posner Paradigm tasks

Visits 8-10 (weeks 1 - 3 of washout phase)

- 1. Side effects will be assessed via MyCap survey at the end of each week of the washout phase
- 2. Weekly assessment of mood using the CES-D questionnaire participants will be prompted to complete this questionnaire at home using the HIPAA compliant Redcap software
- 3. Daily assessment of irritability symptoms using the irritability subscale of the IDAS questionnaire participants will be prompted to complete this questionnaire at home using the HIPAA compliant Redcap software

Visits 11 - 13 (weeks 1 - 3 of Condition 2)

- 1. Side effects will be assessed by phone at the end of weeks 1-2 or in person at the end of week 3 during the home visit to collect urine strips.
- 2. Weekly assessment of mood using the CES-D questionnaire participants will be prompted to complete this questionnaire at home using the HIPAA compliant Redcap software
- 3. Daily assessment of irritability symptoms using the irritability subscale of the IDAS questionnaire participants will be prompted to complete this questionnaire at home using the HIPAA compliant Redcap software

4. At the end of week 3 of Condition 2, participants visit the lab in at the end of baseline week 4 (+/- 2 days from day 21 of the Condition 2) and undergo EEG testing with Dot Probe and the Affective Posner Paradigm tasks

Visit 14 (Progesterone Follow-up Phase)

1. Research staff will follow participants for up to 28 days or until bleeding ceases to document onset, duration and magnitude (degree of flow) of the progesterone-induced menstrual bleed

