Psychiatric History will be determined by in-person interview using the Mini International Neuropsychiatric Interview (MINI) screens. Research staff will be trained by [name] to conduct the interview using the MINI training protocol that is used in [name] laboratory. All MINIS will be recorded, and [name] will review each MINI with the research staff member who conducted the interview to determine a consensus diagnosis. The audio recordings will be reviewed when needed to arrive at the diagnosis.

The Life Events Survey^{32,33}empirically modified to assess only those events that are moderate to severely stressful ("very stressful"), 34–36 will be used to confirm very stressful life events in the preceding 6 months. These include: divorce/separation, serious illness/death of close family member/friend, major financial problems, assault, life threat,

² Study Visits: 0 = enrollment; 1-4 = baseline phase; 5-7 = Condition 1; 8-10 = washout phase; 11 - 13 = Condition 2; 14 = Prometrium follow-up

personal or close relative's arrest for a serious crime. We will require 1+ very stressful life event (60% of our prior perimenopause samples). Other stressful life events (e.g., new job, major move, disagreements) are also assessed. We will administer this scale at the enrollment visit to confirm the presence of 1+ recent very stressful life event.

Outcome Variables:

The following questionnaires will be administered using the REDCap platform and associated participant MyCap app.

We will administer the Inventory of Depression and Anxiety Symptoms (IDAS)³⁷ at enrollment. This 64-item survey assesses ill temper (i.e., irritability), dysphoria, panic, social anxiety, appetite, lassitude, suicidality, well-being, traumatic intrusions, and insomnia. The IDAS has excellent psychometric properties and is validated in reproductive mood disorders.³⁷ Symptoms items for each scale are rated 1 (not at all) to 5 (extremely). The total IDAS score may range from 64 - 320 reflecting general level of psychological distress. Clinical cut points with diagnostic predictability have been established for Major Depressive Disorder (score \geq 32.5), Panic Disorder (score \geq 37.5), Post Traumatic Stress Disorder (score \geq 37.50), and Generalized Anxiety Disorder (score \geq 35.5).

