We will administer the Center for Epidemiologic Studies Depression Scale (CES-D) weekly throughout the study. The total CES-D score may range from 0–60 reflecting level of depressive symptoms. A clinical cutpoint for Major Depressive Disorder has been established (score ≥16). We will monitor the weekly CES-D submissions and use scores at these levels to warrant follow-up by [name] or [name] to assess psychological distress and determine if the participant is able to continue in the study.

The **5-item ill temper scale of the IDAS will be the primary measure of irritability** and will be used at enrollment to ensure at least moderate levels of irritability, and daily to examine associations with E1G variability and EEG measures. **We will require an ill temper score of >10** (range 5-25), consistent with [name] preliminary data showing perimenopausal depressed women with levels of 11 on this scale are responsive to TE2.

The Behavioral Inhibition/Behavioral Activation Systems (BIS/BAS) 38 (RDoC Matrix) is comprised of 20 items. Respondents answer with a 1 – 4 scale (the statement is 1 = very true for me vs. 4 = very false for me). Lower scores reflect more agreement with the statement. This survey has five subscales that assess:

- 1) Behavioral activation (BAS, impulsivity) five item subscale with scores ranging from 5 20
- 2) Reward Responsiveness five item subscale with scores ranging from 5 20
- 3) Fun Seeking four item subscale with scores ranging from 4 16
- 4) Behavioral inhibition (BIS, anxiety) seven item subscale with scores ranging from 7 28.

We also include the 5-item $\frac{\text{Frustrative Non-reward Responsiveness Subscale}}{\text{Mon-reward Responsiveness Subscale}}$ (RDoC Matrix) to quantify approach motivation following FNR. This subscale is imbedded in the BIS/BAS instrument with lower scores reflecting greater frustration to non-reward. The scores range from 5-20.

We will administer these scales immediately before the two EEG tasks designed to activate threat/anxiety (the Dot Probe task) and frustration to non-reward (the Affective Posner Paradigm) at baseline Visit 4 and again at end of Condition 1 (Visit 7) and Condition 2 (Visit 13).

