7.8. Early Discontinuations

Data to be Collected

If a participant chooses to withdraw consent or discontinue with the study interventions no medical records data will be collected at any point, however the following procedures will employed:

- 1. We will ask participant the reason for their withdrawal and record that in in their file and in the study database
- We will attempt to meet with the participant for one last visit to collect used/unused patches to determine compliance up to that point, assess and document vitals, and collect any E1G stored or unused urine strips.
- 3. If the participant wishes to withdraw from the intervention conditions, we will ask if they remain willing to complete the self-report surveys, particularly the irritability symptom scale on a daily basis, throughout the remainder of time that would correspond to their 14 study visits as irritability symptomatology is the primary outcome variable.
- 4. If the participant withdraws during or after at least one of the Conditions (TE2 or Placebo), the study gynecologist, [name] will be unblinded and determine if the participant needs the progesterone intervention for uterine protection. If that is determined to be the case, in order to

maintain the blind for research staff and the PI, [name] will be the one to follow the participant and document menses onset, duration, and magnitude associated with the Prometrium.

Criteria for Intervention Discontinuation

An individual will be withdrawn from the study by the investigators under any of the following conditions:

- 1. Inability to tolerate the adhesive in the patches
- 2. If there is indication of psychological distress that impairs function and would warrant treatment. We will monitor the CES-D in real time, on a weekly basis. If the clinical cut point with diagnostic specificity for Major Depressive Disorder (score ≥ 16), [name] will follow-up to assess psychological distress and determine if the participant is able to continue in the study. [name] will determine the next course of action (i.e., participant may continue or will be withdrawn and referred to the UNC Center for Women's Mood Disorders)

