- 3. Emergent suicide ideation with intent or suicide behaviors. We will monitor the suicide questions (#s 14, 15) on the CES-D in real time, on a weekly basis. #14: I thought about my own death; #15: I thought about hurting myself. Question #14: I wished I were dead; #15: I wanted to hurt myself. Although endorsing these questions in and of themselves does not indicate imminent risk for suicide behaviors, a response of 4 on a 1 5 scale on any of these items (0 = not at all or less than 1 day; 2 = 1-2 days; 3 = 3-4 days; 4 = 5-7 days; 5 = nearly every day for the past week) will trigger a review by [name], who holds a master's in counseling psychology, or [name]. They will use their clinical judgement based on the number of other suicide risk items endorsed and the magnitude of thoughts or experiences (scores of 4 5) to determine if a follow-up assessment is warranted to ascertain more detail about these thoughts, including suicide intent and access to means. Someone with suicide ideation with intent or who has engaged in suicide behaviors will be withdrawn and referred for treatment.
- 4. Start of an exclusionary medication. At each study visit we will ask if the participant has started or stopped any medication or hormonal agent. The research staff will compare with the list of allowable and exclusionary medications.
- 5. Failure or inability to comply with study procedures as determined by the staff and ultimately by [name].
- Development of an exclusionary condition such as migraine with aura, deep vein thrombosis, diabetes.

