12.3. Assessment of Safety

- Side effects and AEs will be assessed at enrollment (in order to obtain a baseline levels of symptoms that
 may represent AEs in response to TE2) and again at baseline week 4 and weekly throughout the
 remainder of the study
- Vitals (blood pressure and weight) will be assessed at enrollment.
- Suicidality will be assessed during the enrollment with the MINI and weekly throughout the protocol using the suicide questions of the CES-D.
- Mood symptoms are assessed at enrollment with the IDAS and weekly with the CES-D throughout the protocol.
- Bleeding patterns are assessed at enrollment and again at weekly throughout the remainder of the study. At
 enrollment, if a participant reports experiencing prolonged menstrual periods (> 7 days) or profuse bleeding
 ('flooding' or bleeding through protection), [name] will perform an ultrasound of the endometrium to

determine if there is evidence of endometrial hyperplasia. In the event this is determined, the participant will be withdrawn from the study and referred for gynecological care.

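### Section 7.4 names the IDAS instead of the CES-D at Visits 5-7, and the Table of Events has no CES-D row, so two weekly CES-D safety triggers have no scheduled input in Condition 1

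*Combined protocol and SAP*

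**What the plan says.** Three sections set the CES-D as the weekly safety instrument. Section 4.3 schedules it weekly for the whole study, gives 16 as the cut-point for major depression, and adds: "We will monitor the weekly CES-D submissions and use scores at these levels to warrant follow-up". Section 7.8 builds two discontinuation criteria on it. For psychological distress it says "We will monitor the CES-D in real time, on a weekly basis", with follow-up at 16 or more. For suicidality it says "We will monitor the suicide questions (#s 14, 15) on the CES-D in real time, on a weekly basis", and a response of 4 prompts a clinical review. Section 12.3 repeats the requirement: "Suicidality will be assessed during the enrollment with the MINI and weekly throughout the protocol using the suicide questions of the CES-D". The next item in 12.3 places the IDAS at enrollment and the CES-D weekly.

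The operational schedule differs. In Section 7.4 the weekly item for Visits 1-4, 8-10 and 11-13 reads "Weekly assessment of mood using the CES-D questionnaire". For Visits 5-7 it reads "Weekly assessment of mood using the IDAS questionnaire", and no other item in that block mentions the CES-D. The Table of Events (7.1) marks an IDAS row at Visits 0-13, and its legend includes "IDAS – Inventory of Depression and Anxiety Symptoms". It has neither a CES-D row nor a CES-D legend entry. Table 1 in Section 4.3 does not list the CES-D either.

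**The concern.** Coordinators work from the visit list and the Table of Events, and 7.4 says participants are prompted to complete the questionnaires in REDCap. A prompt schedule built from 7.4 would leave the CES-D out of Condition 1. One built from the Table would leave it out everywhere.

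Condition 1 is the first exposure to blinded treatment, with about half the women on active TE2. Section 12.2 admits women with mild current suicide ideation without intent, and it names undetected worsening of mood as a risk of participation. If the CES-D is missing in these weeks, the two score-based reviews in 7.8 cannot be triggered, although they could be in Condition 2. At stake is whether the safety rules apply consistently. The efficacy analysis is not affected, because the CES-D is not an outcome in either aim.

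**Working it through.** There is no power or alpha figure to reproduce. The check sets the stated schedules side by side for the 13 weekly visits from baseline to the end of Condition 2, leaving aside the daily ill temper rating.

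| Visits | Phase | 7.4 | Table of Events | 4.3, 7.8, 12.3 |
|---|---|---|---|---|
| 1-4 | Baseline | CES-D | IDAS | CES-D |
| 5-7 | Condition 1 | IDAS | IDAS | CES-D |
| 8-10 | Washout | CES-D | IDAS | CES-D |
| 11-13 | Condition 2 | CES-D | IDAS | CES-D |

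**CES-D coverage.**
- Required by 4.3, 7.8 and 12.3: 13 of 13 visits.
- Named in 7.4: 4 + 3 + 3 = 10 of 13. Missing: 13 - 10 = 3, which is all of Condition 1.
- Named in the Table of Events: 0 of 13.

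**Exposure if 7.4 is followed literally.** Section 5.1 expects about 35 women to enter the cross-over and 30 to complete. Ignoring dropout, the woman-weeks without CES-D are 35 x 3 = 105 (30 x 3 = 90 for completers).

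**Coverage by any mood instrument.** Under 7.4 this is 10 CES-D + 3 IDAS = 13 of 13. Under the Table it is 13 IDAS, and under 4.3 and 12.3 it is 13 CES-D. No stated schedule leaves a week without an instrument.

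**Can the IDAS stand in for the CES-D triggers?** Section 4.3 describes the IDAS as follows: "This 64-item survey assesses ill temper (i.e., irritability), dysphoria, panic, social anxiety, appetite, lassitude, suicidality". It gives cut-points for four diagnoses: major depression (32.5), panic disorder (37.5), PTSD (37.5) and generalized anxiety disorder (35.5). It gives none for suicidality. The reporting procedures that follow 12.5 tell staff to watch the IDAS cut-points and the suicide subscale, but set no score for that subscale. Nothing in the documents maps an IDAS score to a CES-D total of 16 or to a response of 4 on items 14 and 15. The IDAS therefore gives some coverage in Condition 1 but cannot operate the two triggers in 7.8.

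**The case against.** The strongest reply is that the controlling text is clear. Sections 4.3, 7.8 and 12.3 each require the CES-D weekly, and 7.4 itself names it in every other phase. One wrong instrument name in one visit block may be a drafting slip, and site staff may well give the CES-D anyway. This stands as a limit on likelihood: 105 woman-weeks is what literal use of 7.4 would cost, not an expected loss. It also concedes that 7.4 and the Table need correcting.

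A reader might infer that Condition 1 is unmonitored, or that withdrawal for mood can only follow a CES-D result. The documents support neither. The IDAS at Visits 5-7 includes suicidality, and side effects are assessed every week. Appendix 5 lists withdrawal and referral among the possible actions after an IDAS cut-point is reached. At their core, the 7.8 criteria concern distress that impairs function and suicide ideation with intent or suicide behaviors; the CES-D is the means of detecting these. What could be lost is two specific triggers, not the whole safeguard.

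A reader might also infer that the remedy is a full IDAS every week in all phases, because the Table marks it and several AE rules use it. Sections 4.3 and 12.3 point the other way by placing the 64-item form at enrollment. The weekly irritability scores in Sections 3 and 8.3 need only the 5-item ill temper scale, so 64 - 5 = 59 items serve no irritability estimand.

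**Conclusion.** The inconsistency is real and should be corrected. As written, 7.4 provides the CES-D at 10 of 13 weekly visits and omits it throughout Condition 1, and the Table of Events omits it altogether. Two triggers in 7.8 therefore have no scheduled input in the three weeks when women first receive blinded treatment. The size, up to 105 woman-weeks, assumes that 7.4 is followed to the letter, that 35 women enter the cross-over and that none drop out. If staff follow 4.3, 7.8 and 12.3 instead, nothing is lost and the correction is purely textual. The point concerns the consistency of safety monitoring and leaves the estimands, power and randomization untouched. It does not show that mood goes unmonitored in Condition 1, since the IDAS, the weekly side-effect checks and the Appendix 5 route give partial cover.

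**What to change.** In 7.4, name the CES-D as the weekly questionnaire at Visits 5-7, as in the other phases. Add a CES-D row marked at Visits 1-13, and a legend entry, to the Table of Events. Section 4.3 could be read as extending the weekly CES-D into the progesterone follow-up, while 12.2 speaks of a 13-week protocol, so one clause saying whether Visit 14 is included would help.

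The cost is one line and one table row. Participants complete at most three more CES-D forms each, and none if the CES-D is already given weekly.

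Do not make the full 64-item IDAS weekly in all phases as part of this correction. Compared with 7.4 it would add 13 - 3 = 10 forms, or 10 x 64 = 640 items per woman. The sponsor should decide separately whether the IDAS-based AE rules (the Grade 2 examples in 12.4, the reporting procedures and the moderate-event row in Appendix 5) keep a weekly IDAS or move to the CES-D. Until that is settled, adding the CES-D at Visits 5-7 should not be taken as an instruction to remove the IDAS there, because those rules draw on it.
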